Protocol Number	RBI.2017.002
Name of Study Device	PROVANT [®] Therapy System
Phase of Development	III
Objective	To demonstrate the analgesic efficacy of PEMF treatment compared to sham treatment in patients with painful diabetic distal symmetric peripheral neuropathy (DSPN) when treatment is administered 30 minutes twice daily through a 120-day period (4 months) (Part A). An 8-month open-label active treatment extension period is included to collect longer-term data on pain, medication use, quality of life and safety (Part B).
Study Design	Part A of this trial is a multi-center, prospective, double-blinded, sham-controlled, randomized clinical trial conducted on subjects with painful diabetic distal symmetric peripheral neuropathy. Part B of this trial is an 8-month single-arm, open-label, active treatment extension period upon completion of Part A. Eligible subjects will include those between 22 and 80 years of age with documented Type 1 or Type 2 diabetes having persistent pain related to diabetic neuropathy in the lower extremities, despite previous treatment(s). Subjects will be assessed with the Toronto Clinical Neuropathy Score at screening, to evaluate the severity of peripheral neuropathy for inclusion. Eligible subjects will be entered into a 14-day ePRO diary run-in period to collect average baseline pain scores related to their diabetic neuropathy in the lower extremities, diary compliance, and analgesic consumption (maintenance and prn prescribed peripheral neuropathic pain medication pill counts). Subjects will collect electronic patient-reported outcome (ePRO) data each morning around the same time during the run-in period. Only those subjects having a mean pain intensity in the lower extremities of \geq 4 and <9 on an 11-point numeric pain rating scale (NPRS) and a diary compliance score of \geq 70% during the 14- day run-in period will be eligible. Subjects will return to the clinic at Baseline (Day 0) for review of eligibility, diary compliance, average baseline diabetic

neuropathic pain score of ≥ 4 and ≤ 9 (calculated as the average of the last 7 days preceding the enrollment visit), and review of stable analgesic pain consumption profile during the 14-day runin period. Qualified subjects based on diary compliance and average pain score will be randomized 1:1 (active: sham) and will be instructed to self-treat twice daily (morning and evening; 8am \pm 2 hours and 8pm \pm 2 hours) for 120 days. Subjects will record electronic patient-reported outcome (ePRO) data following each morning treatment for 120 days. Subjects consenting to distal thigh and distal leg skin biopsies during the Screening visit will have biopsies collected and sent to the central laboratory for assessment. All subjects will have a baseline Skin Perfusion Pressure (SPP), Sural Nerve Conduction Studies (NCS), Quantitative Sensory Testing (QST), and will complete the Work Productivity and Activity Impairment Questionnaire (WPAIQ), and NeuroOoL.

Subjects will receive a telephone call at Day 7 to ensure compliance to treatment and diary completion, provide followup information on the biopsy sites (if applicable), complete a blinding assessment as well as be assessed for safety and concomitant medication changes.

At **Month 1** subjects will return to the clinic for evaluation of safety, concomitant medication changes, review device usage (reports will be supplied to the site) and ePRO diary completion, and Patient Global Impression (PGI). Treatment satisfaction will also be assessed.

At **Month 2** subjects will return to the clinic for evaluation of safety, concomitant medication changes, treatment satisfaction, review of device usage (reports will be supplied to the site) and ePRO diary completion, quality of life outcomes (WPAIQ and NeuroQoL), Patient Global Impression (PGI), and interim visit measurements of SPP.

At **Month 3**, subjects will return to the clinic for evaluation of safety, concomitant medication changes, review device usage (reports will be supplied to the site) and ePRO diary completion, and Patient Global Impression (PGI). Treatment satisfaction will also be assessed.

At **Month 4** (end of Part A / start of Part B), subjects will return to the clinic for evaluation of safety, treatment satisfaction, review of device usage (reports will be supplied to the site), HbA1c, concomitant medication changes, weight, quality of life

outcomes (WPAIQ and NeuroQoL), PGI, final measurements of SPP, NCS, QST and be assessed to determine their Toronto Clinical Neuropathy Score. Those subjects who consented and had biopsies collected at the Enrollment visit, will have their 4- month study biopsies during this visit and samples sent directly to the central laboratory for assessment. Subjects will return the study device and complete a blinding assessment.
Subjects that complete Part A will continue into the open-label extension period (Part B). All subjects will be reconsented if not completed at a prior visit and given an open-label active device. Subjects will record ePRO data for one week prior to the Month 6, 8, 10, and 12 visits following each morning treatment. Subjects will be reminded of the150-day (Month 5) phone call.
At Month 5 , subjects will receive a telephone call to ensure compliance to treatment, and to be assessed for safety and concomitant medication changes. Subjects will be reminded to record ePRO data for one week prior to the 180-day (Month 6) phone call.
At Month 6 , subjects will receive a telephone call to ensure treatment compliance and collection of diary data, and to assess safety and concomitant medication changes. Subjects will be reminded of the 210-day (Month 7) phone call.
At Month 7 , subjects will receive a telephone call to ensure treatment compliance, and to assess safety and concomitant medication changes. Subjects will be reminded to record ePRO data for one week prior to the 240-day (Month 8) visit.
At Month 8 , subjects will return to the clinic for evaluation of safety, measure QST, treatment satisfaction, review of device usage (reports will be supplied to the site) and collection of diary data, concomitant medication changes, quality of life outcomes (NeuroQoL), and PGI. Subjects will be reminded of the 270-day (Month 9) phone call.
At Month 9 , subjects will receive a telephone call to ensure treatment compliance, and to assess safety and concomitant medication changes. Subjects will be reminded to record ePRO data for one week prior to the 300-day (Month 10) phone call.

	At Month 10 , subjects will receive a telephone call to ensure treatment compliance and collection of diary data, and to assess safety and concomitant medication changes. Subjects will be reminded to record ePRO data for one week prior to the 330-day (Month 11) phone call.
	At Month 11 , subjects will receive a telephone call to ensure treatment compliance, and to assess safety and concomitant medication changes. Subjects will be reminded to record ePRO data for one week prior to the 361-day (Month 12) end of study visit.
	At Month 12 (end of open-label treatment extension), subjects will return to the clinic for evaluation of safety, weight, QST, NCS, TCNSS, PGI, treatment satisfaction, review of device usage (reports will be supplied to the site) and collection of diary data, concomitant medication changes, quality of life outcomes (NeuroQoL), and will return the study device. Subjects who consented and had biopsies collected at the 4 Month visit, will have their end of study biopsies performed during this visit. Biopsy samples will be sent directly to the central laboratory for assessment.
Sample Size	The anticipated enrollment in this study is 170 subjects. The estimate of 85 patients per arm is based on results from a previous trial of PEMF therapy in this patient population.
Study Locations	Up to 20 sites in the United States
Indication	Adjunctive treatment of diabetic neuropathic pain and discomfort.
Visit Schedule	This study includes a total of 8 clinic visits and 7 telephone calls. The visit schedule is as follows:
	• Screening Visit (Day -15)
	• Enrollment Visit (Day 0)
	• Day 7 phone call (+2 days)
	• Month 1 (± 3 days)
	• Month 2 (\pm 3 days)
	• Month 3 (± 3 days)
	• Month 4 (± 3 days) (end of Part A / start of Part B)

	• Month 6 phone call (± 3 days)
	• Month 7 phone call (± 3 days)
	• Month 8 Visit (± 3 days)
	• Month 9 phone call (± 3 days)
	• Month 10 phone call (± 3 days)
	• Month 11 phone call (± 3 days)
	• Month 12 Visit (end of Part B) (± 3 days)
Treatment Arms	Part A - 1:1 Randomization (PEMF 42 μs : Sham) Part B – open-label PEMF 42 μs treatment
Efficacy Endpoints	 Primary Endpoint: Absolute change from baseline in pain intensity as measured by the 11-point, numerical pain rating scale (NPRS) (0-10; where 0=no pain, to 10=worst possible pain) through 4 months.
	 Secondary Endpoints: Percentage of patients who have either a 2 point or 30% reduction in NPRS at 4 Months. Time to 30% or 2-point reduction in NPRS, whichever comes first at 4 Months. Change in neuropathy related quality of life (NeuroQoL) between baseline and end of treatment at 4 Months. Changes in Skin Perfusion Pressure from baseline to end of treatment at 4 Months. Changes in Nerve Conduction Studies of Velocity and/or Amplitude between baseline and end of treatment at 4 Months. Changes in Quantitative Sensory Testing between baseline and end of treatment at 4 Months. Changes in Patient Global Impression at 4 Months.
	 Exploratory Endpoints: Changes in WPAIQ Changes in intraepidermal nerve fiber density (IENFD) at the distal thigh. Changes in IENFD at the distal leg. Evaluation of the NPRS, NCS and NeuroQoL during Part B will be considered avalantees.
Safety Endpoints	 Adverse events, serious adverse events Unanticipated adverse device effects

Γ

Study Device	The study device is the PROVANT [®] Therapy System. The active device will deliver dual field pulsed electromagnetic field energy in the radiofrequency range. The active treatment and inactive sham devices will be identical in appearance and all other physical characteristics in order to maintain the blinding of the treatment. Each device will be identified with a unique kit number.
Inclusion/Exclusion	Inclusion Criteria
	 Subject has documented Type 1 or Type 2 diabetes mellitus according to the ADA criteria (Appendix B).³³ Subject has daily pain attributed to symmetrical lower extremity diabetic peripheral neuropathy for at least 6 months prior to screening, as confirmed by score of ≥ 6 on the Toronto Clinical Neuropathy Scoring System. Subjects' average lower extremity pain related to diabetic peripheral neuropathy over the preceding 24 hours is ≥4 and <9 based on the 11-point NPRS (0-10) at the Screening Visit. Subject age is greater than or equal to 22 years and less than 80 years of age. Subject has an HbA1c ≤10% at Screening or within 3 months of Screening. Subject has an ankle-brachial index (ABI) of ≥0.8 to ≤1.3. If the subject has incompressible vessels, a toe brachial index of 0.8 to 1.3 is required. These adequate lower extremity studies are with no documented intermittent claudication.
	9. Subject walks independently with or without assistive devices, and does not require a wheel chair.

	surgery (related to lower extremity symptoms), or connective tissue disease) within the past 10 years.
6.	Subject has previous or current history of primary or tertiary hyperparathyroidism, hypercalcemia, psychiatric disorder, alcohol dependency, Hepatitis B or C, or HIV infection.
7.	According to the judgement of the Investigator, subject has clinically significant cardiovascular disease within 6 months prior to screening (unstable or poorly controlled hypertension, transient ischemic attack, myocardial infarction, unstable angina, arrhythmia, cardiac surgery, stent placement or angioplasty, or congestive heart failure).
8.	Subject has a history of any uncontrolled medical illness that, in the investigators judgment, places the subject at unacceptable risk for enrollment in a research trial with pulsed electromagnetic field therapy.
9.	Subject requires or anticipates the need for surgery (other than minor day surgical procedures such as dental or minor cosmetic procedures not involving the lower extremities and not requiring extended use of analgesics) or extended travel during the treatment period.
10.	Subject has a total foot depth (most inferior aspect of the medial malleolus to the plantar aspect of the foot when residing on a treatment pad) of >8 cm.
11.	Subject has received any investigational drug or device within 30 days prior to the Screening Visit.
12.	Subject has received long acting lidocaine, marcaine or bupivacaine injection products or other agents for nerve blocks within 6 weeks prior to the Screening Visit.
13.	Subject has used chronic systemic corticosteroid treatment within 3 months of the Screening Visit.
14.	Subject has a history of malignancy within the past 5 years in the treatment area.
15.	Subject has severe mental health or psychiatric disorder of sufficient severity that would interfere with study performance and/or assessments in the opinion of the Investigator.
16.	Subject is receiving prn narcotic medications.
17.	Subject has a known history of drug or alcohol abuse within one year prior to the Screening Visit.

	 Subject has an implanted pacemaker, defibrillator, neurostimulator, spinal cord stimulator, bone stimulator, cochlear implant, or other implanted device with an implanted metal lead(s). 	
	19. Subject is currently pregnant or planning to become pregnant prior to Day 180.	
	20. Treatment of the lower extremity with PROVANT [®] Therapy System.	
	21. Subject is unwilling or unable to follow study instructions or comply with the treatment regimen, diary documentation, and study visits.	
	22. Subject has pain from any other source that can confuse the assessment of the pain associated with DPN.	
	23. Subject has a clinically significant foot deformity (Charcot Neuroarthropathy or Talipes Equinovarus).	
	24. Subject has been diagnosed with mononeuropathy in the distal lower extremities.	
	25. Subject has a skin condition that could alter their peripheral sensation (i.e. exfoliating skin conditions, dermatitis, bruises, weeping skin, skin lesions, infected skin, or necrotic skin) on the feet.	
	26. Subject has had previous surgery to the spine or lower extremity with residual symptoms of pain or difficulty with movement.	
	27. Subject has clinically significant arthropathy (i.e. rheumatoid arthritis, osteoarthritis, gout) that contributes to pain during casual walking or stair climbing.	
Statistical Considerations	All safety analyses will be performed on the intent to treat population from Part A of the study, defined as all subjects who were enrolled into the study and issued a study device when randomized. Once a subject is determined to be eligible, after completion of the run-in period, the subject will be enrolled and randomized into the study and become part of the ITT population.	
	All recorded data will be listed by subject and time point. Descriptive statistics will be tabulated for all randomized subjects for the change from baseline to study day 121, and separately for the change from baseline to the last recorded set of evaluations. The latter should include all subjects who were randomized and completed at least one set of evaluations after randomization.	

A pre-specified sub-group analysis will be performed on subjects with pain scores ≥ 5 as well as subjects with A1C above and below 8.5.

All hypothesis tests comparing active and sham treatment will be two-sided and conducted at the 5% significance level based on Part A of the study. The primary population for assessing efficacy and safety will be the ITT population from Part A. A secondary analysis of the individual efficacy endpoints will be conducted using the Per-Protocol population from Part A. All summary tables will be presented by treatment group and over all patients in the analysis population being summarized. Continuous variables will be summarized using the following descriptive statistics: n, mean, SD, median, minimum, and maximum. Categorical variables will be summarized using counts and percentages. Percentages presented will be calculated using all patients in the analysis population being summarized (with randomized or received treatment as/if appropriate) as the denominator.

To compare the absolute change in pain from baseline to 4months, the intra-patient change will be calculated and serve as the dependent variable in the analysis. The baseline pain score will be introduced in the model as a covariate. Clinical site will be added to the model to assess poolability of the data across sites. Interaction between clinical site and treatment will be evaluated using a type 1 error rate of 10%.

Treatment-emergent adverse events will be summarized by study part, type, frequency, severity, and relationship to the study device. Adverse events will be provided in a listing.

SAS® Version 9.4 or later will be used to produce all statistical tables, listings and figures to be contained in the integrated statistical/clinical report.

Table of Contents

1.	INTRODUCTION AND BACKGROUND	.19
2.	STUDY OBJECTIVES	.24
3.	STUDY DESIGN	.25
3.1	Study Design	. 25
3.2.	EFFICACY ENDPOINTS	.26
3.3	SAFETY EVALUATION	.26
3.4	Eligibility Criteria	. 27
3.5	ENROLLMENT	. 30
3.6	RANDOMIZATION	. 30
3.7	DEVICE DESCRIPTION	. 30
3.7.1	Control Unit	. 30
3.7.2	Treatment Applicator	. 32
3.8	LOGISTICS AND DEVICE ACCOUNTABILITY	. 32
3.9	LABELING	. 33
3.10	Preparation and Administration	. 33
3.11	Blinding	. 33
3.12	Study Assessments	. 34
3.12.1	Primary Efficacy Assessment	. 34
3.12.2	Secondary Efficacy Assessments	. 34
3.12.3	Exploratory Efficacy Assessment	.37
3.12.4	Additional Study Assessments	. 38
3.12.5	Safety Assessments	. 40
4.	STUDY PROCEDURES	.40
4.1	VISIT 1 – SCREENING VISIT (DAY -15)	.40
4.2	14-Day Run-In Period	.42
4.3	Visit 2 – Enrollment Visit (Day 0)	.42
4.4	Day 7 Phone Call (Day 7 +2 Days)	.43

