Ho: μ (Change in NPRS score at 4 months / PEMF group) = μ (Change in NPRS score at 4 months / sham group)

Ha: μ (Change in NPRS score at 4 months / PEMF group) $\neq \mu$ (Change in NPRS score at 4 months / sham group)

To compare the absolute change in pain from baseline to 4-months, the intra-patient change will be calculated and serve as the dependent variable in the analysis. The baseline pain score will be introduced in the model as a covariate. Clinical site will be added to the model to assess poolability of the data across sites. Interaction between clinical site and treatment will be evaluated using a type 1 error rate of 10%.

Mixed Models with Repeated Measures (MMRM) comparing results across all time-points will also be performed, adjusted for the baseline value, week, treatment by week interaction and the effect of the patient.

Sub-group analysis will be pre-specified in the SAP and will be performed on subjects with pain scores ≥ 5 as well as subjects with A1C above and below 8.5.

Missing or Incomplete Data

If a patient reports at least 3 days with non-missing pain intensity scores within a particular week, the weekly mean pain intensity score will be derived using the non-missing scores only. This is identical to imputing the missing scores as the mean of the non-missing scores. If the patient reports less than 3 days with non-missing pain intensity scores within a particular week, the weekly mean pain intensity score will be treated as missing data.

Missing weekly mean pain intensity scores will be imputed using multiple missing data and pattern mixture methodology. Sensitivity analyses will be conducted exploring different patterns for missing data. An MMRM will be performed using only observed data without multiple imputation

and an analysis using the change from baseline to the last non-missing weekly mean pain intensity score will also be provided.

The pattern mixture model methodology will be implemented using SAS procedures MI and MIANALYZE. Specifically, the following steps will be followed:

• Intermittent missing data will first be imputed using the Markov Chain Monte Carlo (MCMC) method implemented with the SAS MI procedure, which is appropriate for non-monotonic missing data.

Data for patients who discontinues early will be multiply imputed as follows:

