3.1.1. Efficacy Assessments and Endpoints

There will be 11 total endpoints from Part A of the protocol (Part B analysis is in a separate SAP); the interest will be in the change from baseline and the differences between active Provant therapy vs. sham.

Primary Endpoint: Absolute change from baseline in pain intensity as measured by the 11-point, numerical pain rating scale (NPRS) (0-10; where 0=no pain, to 10=worst possible pain) through 4 months.

Secondary Endpoint 1: Percentage of patients who have either a 2 point or 30% reduction in NPRS at 4 Months.

Secondary Endpoint 2: Time to 30% or 2-point reduction in NPRS, whichever comes first at 4 Months.

Secondary Endpoint 3: Change in neuropathy related quality of life (NeuroQoL) between baseline and end of treatment at 4 Months.

Secondary Endpoint 4: Changes in Skin Perfusion Pressure (SPP) from baseline to end of treatment at 4 Months.

Secondary Endpoint 5: Changes in Nerve Conduction Studies (NCS) of Velocity and/or Amplitude between baseline and end of treatment at 4 Months.

Secondary Endpoint 6: Changes in Quantitative Sensory Testing (QST) between baseline and end of treatment at 4 Months.

Secondary Endpoint 7: Change in Patient Global Impression (PGI) at 4 Months.

Exploratory Endpoint 1: Change in Work Productivity and Impairment Questionnaire (WPAIQ) **Exploratory Endpoint 2:** Changes in intraepidermal nerve fiber density (IENFD) at the distal thigh.

Exploratory Endpoint 3: Changes in IENFD at the distal leg.

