The Level 3 displays will report the paired results for the change from the baseline through Month 4. For example, if 18 subjects complete the baseline evaluation and 16 subjects complete the Month 4 visit, the difference (Month 4 minus Baseline) will contain 16 subjects.

Supportive individual subject data listings will be sorted and presented by subject number and visit date, if applicable. Listings will also include the number of days relative to the initial study treatment (active or sham).

Specific algorithms are discussed for imputing missing or partially missing dates, if deemed appropriate, under specific data topics. Imputed or derived data will be flagged in the individual subject data listings. Imputed data will not be incorporated into any raw or primary datasets. The imputed data will be retained in the derived / analysis datasets.

The total duration for a subject *on-study* will be calculated as the difference between the date of initial study treatment (active or sham) and the last day of observation plus 1 day. All calculations for defining the duration on-study will follow the algorithm DURATION = [STUDY COMPLETION OR WITHDRAW DATE – INITIAL TREATMENT DATE + 1].

This section details general conventions to be used for the statistical analyses. The following conventions will be applied to all data presentations and analyses.

- Summary statistics will consist of the count and percentage in each level for categorical variables, and the sample size (n) mean, median, standard deviation (SD), minimum, and maximum values for continuous variables.
- All mean and median values will be formatted to one more decimal place than the measured value. Standard deviation values will be formatted to two more decimal places

than the measured value. Minimum and maximum values will be presented with the same number of decimal places as the measured value.

- The number and percentage of responses will be presented in the form XX (XX.X%).
- All probability values will be rounded to four decimal places. All p-values that round to 0.0000 will be presented as '<0.0001' and p-values that round to 1.0000 will be presented as '>0.9999'. P-values <0.05 will be considered to be statistically significant.
- All summary tables will include the analysis population sample size (i.e., number of subjects).

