7.2. Handling of Dropouts or Missing Data

Missing data may have an impact upon the interpretation of the trial data. Values for missing data will not be imputed, however a methodology is defined for missing dates. All available data for subjects who do not complete the study will be included in the data listings. An analysis of the last recorded observation will be conducted to facilitate a comparison predicated on the ITT population.

Safety Data

Missing or incomplete data will not be imputed. For patients who withdraw from the study prematurely, the last recorded observation will serve as final observation.

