- All tables, figure, and data listings will have the name of the program and a date/time stamp on the bottom of each output.
- Population sizes may be presented for each treatment or dosing category as totals in the column header as (N=xxxx), where appropriate.
- Population sizes shown with summary statistics are the samples sizes (n) of patients with non-missing values.
- All population summaries for categorical variables will include categories that the patients had a response in these categories.
- All percentages are rounded and reported to a single decimal point (xx.x%).

November 7, 2018

• Population summaries that include p-values will report the p-value to three decimal places with a leading zero (0.001). All p-values reported on default output from statistical software (i.e., SAS® Software) may be reported at the default level of precision. P-values <0.001 should be reported as <0.001 not 0.000.

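### For Secondary Endpoint 1 (2-point or 30% NPRS responder at Month 4), the general rules conflict and neither document says how subjects without a Month 4 score are counted

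*Protocol*

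**What the plan says.** SAP 3.1.1 defines Secondary Endpoint 1 as "Percentage of patients who have either a 2 point or 30% reduction in NPRS at 4 Months". The protocol synopsis lists the same endpoint first among the secondaries.

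On who is counted, the protocol synopsis (Statistical Considerations) says "The primary population for assessing efficacy and safety will be the ITT population from Part A" and, for categorical summaries in general, "Percentages presented will be calculated using all patients in the analysis population being summarized".

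On missing scores, Protocol 7.1 says "Missing weekly mean pain intensity scores will be imputed using multiple missing data and pattern mixture methodology". A week with fewer than 3 diary scores is missing. Subjects who stop for an adverse event or lack of response are imputed from a distribution like their arm's baseline. Subjects who stop for other reasons are imputed from those in the same arm who are still in the study. Protocol 7.1 also plans an observed-data MMRM and an analysis of the last non-missing weekly mean.

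SAP 7.2 says "Values for missing data will not be imputed, however a methodology is defined for missing dates", and then "An analysis of the last recorded observation will be conducted to facilitate a comparison predicated on the ITT population". Two further SAP conventions touch the question. Section 13.1 says "Population sizes shown with summary statistics are the samples sizes (n) of patients with non-missing values". Section 7 illustrates a change-from-baseline table in which 18 subjects have a baseline, 16 have Month 4, and "the difference (Month 4 minus Baseline) will contain 16 subjects". The responder table itself (Table 14.4.1.1.4, SAP 11) has a title, with no denominator and no status for dropouts.

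**The concern.** Two programmers could each follow one document and report different responder rates from the same data. One keeps all ITT subjects in the denominator and uses imputed weekly means. The other imputes nothing, and either analyses only subjects with a Month 4 value or carries the last recorded observation forward. The last route can label as a success at 4 months someone who stopped treatment long before.

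Missing Month 4 scores should be common. Protocol 7.4 assumes 30% premature discontinuation, and Protocol 5 collects no further data after withdrawal. Under the hierarchy in Protocol 7.1, this endpoint is tested first among the secondaries, so its result affects whether the later ones are tested. (SAP 7.3 applies no multiplicity adjustment, which is a separate inconsistency.) With the rule unstated, it could be chosen after the dropout pattern is known.

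**Working it through.** **The plan's own figure.** None is given for the responder endpoint. The inputs borrowed below come from the sample size in Protocol 7.4, which reproduces: 2 × (1.960 + 1.282)² × 1.83² / 1.07² = 61.5, so 62 per arm.

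**One subject under each candidate rule.** Take a subject whose pain fell by more than 2 points early on and who then left for an adverse event.

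- All-ITT denominator, no value supplied: in the denominator, not in the numerator.
- Observed case: in neither.
- Last recorded observation: in both, as a responder.
- Protocol 7.1 multiple imputation: in the denominator, with Month 4 values drawn from a baseline-like distribution, so rarely a responder. Had the subject left for another reason, the draws would resemble those still in the arm.

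**Illustration 1: assumed completer response of 50% active and 35% sham.** With dropouts as non-responders, the all-ITT rate is completer rate × (1 − dropout).

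- Active arm at 30% dropout: 0.50 × 0.70 = 35%.
- Difference at 30% / 30%: 0.50 × 0.70 − 0.35 × 0.70 = 10.5 points.
- Difference at 35% active / 25% sham: 0.50 × 0.65 − 0.35 × 0.75 = 6.25, about 6.3 points.
- Difference at 25% active / 35% sham: 0.50 × 0.75 − 0.35 × 0.65 = 14.75, about 14.8 points.

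The observed-case difference is 15 points throughout, by construction. If imputed dropouts respond at the completer rate, the active rate at 30% dropout is 0.50 × 0.70 + 0.50 × 0.30 = 50%. With baseline-like draws it falls toward 35%.

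**Illustration 2: completer rates from the documents' own means.** Protocol 7.4 gives an active mean reduction of 1.79 and SD 1.83. The sham mean is 0.40 × 1.79 = 0.716. Assume normal changes and use the 2-point cut only:

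- Active: 1 − Φ((2 − 1.79)/1.83) = 45.4%.
- Sham: 1 − Φ((2 − 0.716)/1.83) = 24.1%.

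There are 85 per arm, and counts are rounded to whole subjects. For last observation, 25% or 50% of dropouts in each arm are assumed to be responding when they leave. Cells show counts active vs sham, the difference in points, and the uncorrected chi-square p.

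| Dropout active / sham | Observed case | All ITT, dropouts non-responders | Last observation, 25% | Last observation, 50% |
|---|---|---|---|---|
| 30% / 30% | 27/59 vs 14/59; 22.0; 0.012 | 27/85 vs 14/85; 15.3; 0.020 | 33/85 vs 20/85; 15.3; 0.031 | 40/85 vs 27/85; 15.3; 0.041 |
| 40% / 20% | 23/51 vs 16/68; 21.6; 0.013 | 23/85 vs 16/85; 8.2; 0.20 | 31/85 vs 20/85; 12.9; 0.066 | 40/85 vs 24/85; 18.8; 0.011 |
| 20% / 40% | 31/68 vs 12/51; 22.1; 0.013 | 31/85 vs 12/85; 22.4; 0.0008 | 35/85 vs 20/85; 17.6; 0.014 | 39/85 vs 29/85; 11.8; 0.12 |

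Fisher's exact test, which the SAP's sample code for proportions reads off, gives 0.020, 0.031, 0.046 and 0.059 for the first row.

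**The case against.** Several stronger readings are tempting, and the documents do not support them.

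- A reader might infer that the SAP uses a non-missing denominator for responder percentages. It never says so. SAP 13.1 concerns the n displayed beside summary statistics, the 16-of-18 example in SAP 7 is a continuous paired change, and SAP 7 also requires each summary table to show the analysis population size. These lean toward observed cases but do not fix a rule. The index of tables is in a separate file that is not among the documents.
- A reader might infer that the protocol's all-patients rule makes dropouts non-responders. A denominator rule does not classify anyone, and Protocol 7.1 would give dropouts an imputed Month 4 value.
- A reader might treat last observation as an SAP departure or a rival denominator. The protocol plans it too (synopsis and 7.1), and it keeps an ITT denominator. It changes who is in the numerator. SAP 7.2 does not name it as the analysis of this endpoint.
- Illustration 1 does not show that the observed-case version is biased. It holds that difference fixed and shows the all-ITT version moving. Whether observed cases mislead depends on outcomes nobody sees.
- Non-responder classification is one defensible choice among several. Adopting it in the SAP alone would create a new mismatch with Protocol 7.1.

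All of these stand as limits on the point. They do not remove it: the stated rules still conflict (imputation in Protocol 7.1, none in SAP 7.2), and nothing settles the matter for this endpoint.

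**Conclusion.** The point holds as a conflict of general rules with no endpoint-specific rule to resolve it. The sharpest part is multiple imputation in Protocol 7.1 against no imputation in SAP 7.2. The SAP's only stated route to an ITT comparison could, if used here, credit early dropouts as Month 4 responders.

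The size is material at the protocol's 30% discontinuation. A 15-point completer difference becomes 10.5 points over all ITT with equal dropout, and 6.3 or 14.8 points with a 10-point imbalance either way. The 50% and 35% rates and the unequal dropout splits are assumptions. The second illustration uses open-label 60-day data, a normal model and the 2-point cut alone.

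A reader might conclude that the choice decides significance. At equal 30% dropout, every version in the table is below 0.05 by chi-square, and one reaches 0.059 by Fisher's test. Clear reversals appear only under the assumed 40% / 20% and 20% / 40% splits, so this is a possibility and not an expected result. The primary endpoint's responder-free comparison of means is not affected by this point. The sponsor should correct it before unblinding.

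**What to change.** In the SAP, under Secondary Endpoint 1 and Table 14.4.1.1.4, state that the denominator is all ITT subjects in each arm and that a subject without a valid Month 4 weekly mean is a non-responder. Define a valid weekly mean by carrying the protocol's rule of at least 3 diary days into the SAP, which lacks it. Align Protocol 7.1 so that its multiple imputation is not read as the main analysis of this endpoint. Report the observed-case, last-observation and multiple-imputation versions as sensitivity analyses only, and show dropout by arm and reason beside them.

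The cost is a few sentences in the SAP and a matching change in the protocol, with no new data. Responder rates will be lower in both arms, and the difference will move with unequal dropout, as the 6.3 and 14.8 point figures show. The sensitivity analyses are there to make that visible.
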